4.6.4. Vital Signs

Unless otherwise specified, vital signs, including physical and developmental measures: height, height SDS using data from WHO, height velocity, height velocity SDS using data from Kelly 2014, and weight SDS using data from CDC 2022 will be analyzed using safety estimand. The analyses for the double-blind period will be conducted using the SS1. For overall study, including double-blind period, open-label period, and safety follow-up period, the analyses will be provided using the SS2.

If multiple records are taken at the same visit, they will be averaged prior to being used for data summaries and analyses.

Height velocity is defined in "cm/year" unit and will be calculated as change in height from baseline to postbaseline scheduled visits at Week 12, Week 30, Week 42 and Week 52divided by the ratio of number of days between both measurements and 365.25. At Visit 3, height velocity will be calculated using the change from screening visit. In addition to height velocity, height velocity SDS will also be presented at same visits.

An MMRM as described in Section 4.1.5.1 will be used to fit the changes from baseline in vital signs at all scheduled postbaseline visits.

Counts and percentages of patients with treatment-emergent abnormal sitting SBP, sitting DBP, and pulse will be presented by treatment. The criteria for identifying patients with treatment-emergent vital sign abnormalities are stated in Table GPGV.4.3.

Table GPGV.4.3. Categorical Criteria for Abnormal Treatment Emergent Blood Pressure and Pulse Measurements (Flynn JT et al 2017)

Parameter	Low	High
Systolic BP (mmHg)	≤85 and decrease from baseline ≥20 (10-11 years old) ≤90 and decrease from baseline ≥20 (≥12 years old)	≥126 and increase from baseline ≥20 (10-11 years old) ≥136 and increase from baseline ≥20 (12-14 years old) ≥140 and increase from baseline ≥20 (≥15 years old)
Diastolic BP (mmHg)	≤50 and decrease from baseline ≥10 (≥10 years old)	≥82 and increase from baseline ≥10 (10-11 years old) ≥86 and increase from baseline ≥10 (12-14 years old) ≥90 and increase from baseline ≥10 (≥15 years old)
Pulse (bpm)	<60 and decrease from baseline ≥25 (10-11 years old) <50 and decrease from baseline ≥15 (≥12 years old)	>140 and increase from baseline ≥25 (10-11 years old) >120 and increase from baseline ≥15 (12-14 years old) >100 and increase from baseline ≥15 (≥15 years old)

Abbreviation: BP = blood pressure; bpm = beats per minute.

High and Low ranges will be derived based on age at the time of assessment.

Hypertension: There may be an incidence of new hypertension, or the worsening of an existing hypertension. Following are the definitions of the 2 categories.

An incidence of new hypertension is defined as one of the following:

- A new AE of hypertension reported, or
- at least 2 consecutive measurements of elevated BP (BP ≥95th percentile for age, sex, and height, or SBP ≥130 mmHg and/or DBP ≥80 mmHg) on separate visits after baseline in an individual with normal BP at baseline.

A worsening of an existing hypertension is defined as one the following:

 AE of hypertension with worsening severity compared to previous MH or AE reported, or

- at least 2 consecutive measurements of elevated BP (BP ≥95th percentile for age, sex, and height, or SBP ≥130 mmHg and/or DBP ≥80 mmHg) on separate visits after baseline in an individual with previous history of hypertension and normal BP at baseline, or
- at least 2 consecutive measurements of elevated BP above baseline (at least 7 mmHg for SBP and 5 mmHg for DBP) on separate visits after baseline in an individual with elevated BP (BP ≥ 95th percentile for age, sex, and height or SBP ≥130 mmHg and/or DBP ≥80 mmHg) at baseline.

The AE of hypertension will be searched using narrow PTs in Hypertension SMQ (20000147). Summary of incidence of new or worsening of hypertension by treatment will be provided from baseline to Week 30 using SS1 and from baseline to Week 52 using SS2.

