Vital signs	X		X		X		X	X	X				X	Vital sign measurements should be taken before collection of blood samples for laboratory testing, at visits where required. For instructions see Appendix 11, Section 10.11.
Height (cm)	X		X		X		X	X	X				X	Triplicate measurements must be in centimeters. For instructions see Appendix 11, Section 10.11.
Weight (kg)	X		X		X		X	X	X				X	Measurements must be in kilograms. For instructions see Appendix 11, Section 10.11.
Calculation of BMI	X													
Waist circumference (cm)			X		X		X	X	X				X	Measurements must be in centimeters. For instructions see Appendix 11, Section 10.11.
Visual acuity checks and dilated fundoscopic examination		X												Visual acuity checks and dilated fundoscopic examination will be scheduled between Visit 2 and Visit 3 only after review of laboratory results from Visit 1 (except for GAD65, Islet cell Ab results if sent and pending at Visit 2) and participant qualifying in all other criteria. The exam will be performed by an eye care professional (ophthalmologist or optometrist) for all participants. A previous exam ≤90 days of screening meeting study requirements is acceptable to confirm eligibility. Additional visual acuity checks and dilated fundoscopic examinations should be performed when clinically indicated by any suspicion of worsening retinopathy. See Section 8.3.3.6.

Study I8F-MC-GPGV											Notes			
	Clinic	Clinic	Clinic	Phone	Clinic	Clinic	Clinic	Clinic	Clinic	Phone	Phone	Clinic	Clinic	Type of visit.
						CCI						CCI		Any phone visit may be converted to a clinic visit if
												_		deemed medically necessary by study personnel.
Visit	V1	V2	V3	V4	V5	V6	V7	V8	V9	V10	V11	V12	V13	CCI
Week	-4	-2	0	1	4	7 a	8	12	16	20	24	29ª	30	
Allowed Visit Intervals (D)		±7	_	±3	±7		±7	±7	±7	±7	±7		±7	
Fasting Visit			X				X		X					Participants should fast at least 8 hours without eating, drinking (except water), or performing any significant physical activity. The dose of insulin on a fasting visit may be temporarily adjusted upon clinical judgment of the investigator.
ECG			X										X	Vital Signs should be taken before ECG, see Section 8.2.6.

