# **1.3.2. Open-Label and Follow-up Period SoA** Perform procedures as indicated.

FhStudy I8F-MC- GPGV			Open-	Label Per	iod			Follow-up Period	Notes
	Phone	Clinic	Phone	Clinic	Phone	Clinic	Clinic	Clinic	Type of visit. Any phone visit may be converted to a clinic visit if deemed medically necessary by study personnel.
Visit	V14	V15	V16	V17	V18	V19	ET	V801	
Week	31	34	38	42	46	52		56	
Allowed Visit Intervals (D)	±3	±7	±7	±7	±7	±7		±7	
Fasting Visit						X	X		Participants should fast at least 8 hours without eating, drinking (except water), or performing any significant physical activity. The dose of insulin on a fasting visit may be adjusted upon clinical judgment of the investigator.
Procedures									
Adverse events	X	X	X	X	X	X	X	X	
Concomitant medications	X	X	X	X	X	X	X	X	
Physical Evaluations									
Physical Exam						X	X	X	
Tanner Staging						X	X		Participants who have reached Tanner stage 5 will not be evaluated again.  Tanner staging details in Appendix 9, Section 10.9
Symptom-directed physical exam by physician				X					See Section 8.2.1.
Vital signs				X		X	X	X	Vital sign measurements should be taken before collection of blood samples for laboratory testing, at visits where required. See Appendix 11, Section 10.11
Height (cm)				X		X	X	X	Measurements must be in centimeter. For instructions see Appendix 11 Section 10.11
Weight (kg)				X		X	X	X	Measurements must be in kilogram. For instructions see Appendix 11, Section 10.11
Waist circumference (cm)				X		X	X	X	Measurements must be in centimeter. For instructions see Appendix 11 Section 10.11
Visual acuity checks and dilated fundoscopic examination						X	X		V19 allowable window of ±21 days. ET allowable window of ±21 days. If the ET visit is scheduled within 6 months of the previous visual acuity checks and dilated fundoscopic examination, follow-up exam is not needed.

FhStudy I8F-MC- GPGV	Open-Label Period						Follow-up Period	Notes	
	Phone	Clinic	Phone	Clinic	Phone	Clinic	Clinic	Clinic	Type of visit.  Any phone visit may be converted to a clinic visit if deemed medically necessary by study personnel.
Visit	V14	V15	V16	V17	V18	V19	ET	V801	
Week	31	34	38	42	46	52		56	
Allowed Visit Intervals (D)	±3	±7	±7	±7	±7	±7		±7	
Fasting Visit						X	X		Participants should fast at least 8 hours without eating, drinking (except water), or performing any significant physical activity. The dose of insulin on a fasting visit may be adjusted upon clinical judgment of the investigator.

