4.1.5. Analytical Methods

4.1.5.1. Analysis Relative to Efficacy Estimand

The analysis related to the efficacy estimand from double-blind period (baseline to week 30) will be conducted utilizing data in the EAS1 and from double-blind and open-label periods (baseline to week 52) will be conducted using the data in the EAS2.

For double-blind period, the analysis model for continuous measurements to make mean comparisons *over time* among treatment arms relative to the efficacy estimand will be an MMRM. The response variable of the MMRM model will be the change from baseline of the endpoint. Unless specifically provided, the terms in the model are:

- treatment (placebo, tirzepatide 5 mg, and tirzepatide 10 mg) as a factor
- visit, as discrete time
- treatment-by-visit interaction
- baseline age group (10 to 14 years, or 15 to <18 years) as a factor
- baseline antihyperglycemic medication (metformin only, or basal insulin only, or metformin and basal insulin) as a factor, and
- baseline of the endpoint as a covariate.

Restricted maximum likelihood will be used to obtain model parameter estimates and the Kenward-Roger option will be used to estimate denominator degrees of freedom. A linear contrast, averaging estimates from the individual tirzepatide doses at 30-week visit, will be used to estimate the treatment effect of the combined tirzepatide arms compared with placebo.

An unstructured covariance matrix will be used to model the within-patient errors. If this model fails to converge, the following covariance structures will be tested in order:

- Heterogeneous Toeplitz
- Heterogeneous First Order Autoregressive
- Heterogeneous Compound Symmetry
- Toeplitz
- First Order Autoregressive, and
- Compound Symmetry.

The first covariance structure that converges will be used. For double-blind and open-label periods, a similar MMRM model will be used except with below treatment as a factor:

• treatment (placebo/tirzepatide 5 mg, tirzepatide 5 mg/5 mg, and tirzepatide 10 mg/10 mg)

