Baseline Tanner Stage for Boy Genital	No	G1, G2, G3, G4, G5	
Baseline Tanner Stage for Girl Breast	No	B1, B2, B3, B4, B5	

^a Subgroup analyses are defined in Section 4.7.3 with more details.

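### The Week 30 height and height-velocity comparison gives up precision because the model leaves out sex and baseline Tanner stage, both of which are collected and predict growth at 10 to 17 years

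*SAP*

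**What the plan says.** SAP 1.1 makes comparison with placebo at 30 weeks a secondary objective for height, height SDS and height velocity. SAP 4.6.4 lists the growth measures, among them "height SDS using data from WHO, height velocity, height velocity SDS", and then gives one model sentence: "An MMRM as described in Section 4.1.5.1 will be used to fit the changes from baseline in vital signs at all scheduled postbaseline visits".

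SAP 4.1.5.1 introduces its term list with "Unless specifically provided, the terms in the model are". The list is treatment, visit, their interaction, "baseline age group (10 to 14 years, or 15 to <18 years) as a factor", baseline antihyperglycemic medication, and "baseline of the endpoint as a covariate". SAP 4.6.4 provides nothing different for height. It also does not say whether height velocity, already a rate, is among the changes that this model fits.

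Sex and Tanner stage are available. SAP Appendix 3 lists sex and, for example, "Baseline Tanner Stage for Girl Breast" among the baseline characteristics. Tanner stage is otherwise used only in the shift tables of SAP 4.7.1. Sex is not a stratification factor (Protocol 6.3, SAP 1.2.2).

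On measurement, the height row of the double-blind schedule (Protocol 1.3.1) says "Triplicate measurements must be in centimeters". The matching row of the open-label schedule (Protocol 1.3.2) says "Measurements must be in centimeter. For instructions see Appendix 11 Section 10.11". Neither that row nor the height steps in Appendix 11 give a number of readings. SAP 4.6.4 averages repeats where they exist.

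**The concern.** The model was written for HbA1c and carried over to growth. The protocol itself, in justifying collection of the full date of birth (10.1.4), says that expected height depends on age and sex. At these ages pubertal stage matters too. A two-level age group cannot separate a boy from a girl of 13, or a child early in puberty from one who has finished growing. Those differences therefore stay in the error term.

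Slowed growth is a named developmental-safety question (Protocol 2.3.1), and the only placebo-controlled look at it is Week 30. Precision lost there widens the interval that has to rule out a meaningful effect, although the information that would narrow it is already in the database.

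**Working it through.** **The plan's own figure.** The documents state no SD, power or precision for height. The only power statement concerns HbA1c (SAP 5), and it reproduces: SE = 1.5 × √(1/30 + 1/60) = 0.335; 1.1/0.335 = 3.28; 3.28 − 1.96 = 1.32, giving power 0.907 (0.900 with the noncentral t). Nothing is wrong there, but it says nothing about growth.

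**Inputs.** From the documents: 60 v 30 children for pooled tirzepatide v placebo, and post-baseline heights at Weeks 4, 8, 12, 16 and 30. Assumed: sex difference D in 30-week growth of 1 to 3 cm (10 to 14 y) and 0.5 to 1.2 cm (15 to <18 y); residual SD 1.2 cm; 35% male, so p(1−p) = 0.35 × 0.65 = 0.2275; equal age strata, with their mean growth difference already removed by the age term; growth linear in time.

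**Sex with its visit interaction (or a Week 30 ANCOVA).** One sex coefficient at Week 30 removes the average difference but not the spread of D between age strata:

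- variance without sex = 1.44 + 0.2275 × mean(D²)
- variance with sex = 1.44 + 0.2275 × var(D)
- SE = √(variance × (1/60 + 1/30)) = √(variance × 0.05)

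| Case | D in the two strata (cm) | mean(D²) | var(D) | Variance without | Variance with | SE (cm) | Cut |
|---|---|---|---|---|---|---|---|
| Low | 1.0, 0.5 | 0.625 | 0.0625 | 1.582 | 1.454 | 0.281 to 0.270 | 4.1% |
| Mid | 2.0, 0.85 | 2.361 | 0.331 | 1.977 | 1.515 | 0.314 to 0.275 | 12.5% |
| High | 3.0, 1.2 | 5.220 | 0.810 | 2.628 | 1.624 | 0.362 to 0.285 | 21.4% |

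Error in the recorded heights adds 2e² to both variances. For an assumed e of 0.12 to 0.40 cm that is 0.029 to 0.320, and the cuts become 3.4 to 4.1%, 10.6 to 12.3% and 18.8 to 21.1%. Rounded: about 3 to 21%, mid case 11 to 12%.

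**Sex as a main effect only.** Growth accumulates, so at Week 4 the sex difference is only 4/30 of its Week 30 size. A coefficient common to all visits is pulled towards the early visits, where changes vary least. I took the coefficient β that maximises the likelihood under an unstructured covariance. In the mid case with e = 0.2, β = 0.037 cm, against an average Week 30 difference of 1.425 cm. Then mean((D−β)²) = 2.361 − 2 × 0.037 × 1.425 + 0.001 = 2.257. The Week 30 variance falls from 1.52 + 0.2275 × 2.361 = 2.057 to 1.52 + 0.2275 × 2.257 = 2.034, an SE cut of 0.6%. Over all cases and e from 0.12 to 0.40, the cut is 0.1 to 2.8%.

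**Height velocity.** With an assumed residual SD of 2 to 3 cm/yr, the 95% half-width is 1.96 × SD × √0.05 = 0.88 to 1.31 cm/yr. If sex and Tanner stage explained 10% or 30% of that variance, it would be 0.83 to 1.25 or 0.73 to 1.10. If velocity does go through the MMRM, its baseline value helps little. It spans about 4 weeks (screening to Visit 3), so even with triplicates its error SD is √(2e²/3)/(28/365.25), which is 2.1 to 7.5 cm/yr for e of 0.2 to 0.7 cm.

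**Reading count after Week 30.** Week 30 has triplicates at both ends and is unaffected. If later heights were single readings, the total velocity SD would rise by at most 5.5% at Week 42 and 3.7% at Week 52 (e of 0.2 to 0.7 cm, true SD 2 to 3 cm/yr).

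**The case against.** The best defence is that stratification factors plus the baseline value make a conventional prespecified safety model, and no document requires more. SAP 4.6.4 also reports height SDS and height velocity SDS beside the raw measures, and SAP 4.7.1 tabulates Tanner shifts by sex and arm. On the usual meaning of an SDS, age and sex are then largely dealt with. Much of this stands. The sex argument is confined to raw centimetres and centimetres per year. Baseline height, already a covariate, may absorb some of the variation. Pubertal stage is still not a covariate for height SDS; whether the velocity reference allows for it cannot be checked from the documents.

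Three stronger readings are tempting, and the documents do not support them:

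- A reader might infer that omitting sex and Tanner stage biases the growth comparison. Assignment is randomised, so it does not; chance imbalance is already inside the standard error.
- A reader might expect a large gain from simply listing sex as a covariate. The working shows almost none for height change unless the term varies by visit. Treating all sex-related variance as removable also overstates the gain: in the high case √(1.44/2.628) = 0.74 would suggest 26%, but a single coefficient cannot absorb a different D in each age stratum.
- A reader might infer that open-label heights are single readings and that this damages the growth analysis. The open-label schedule gives no number. After Week 30 placebo children receive tirzepatide, and SAP 4.1.4 rules out between-group comparison at Week 52.

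**Conclusion.** The point holds as a modest loss of precision in the Week 30 analysis of raw height and, if it is modelled the same way, raw height velocity. Under the stated assumptions, sex with its visit interaction would cut the Week 30 height standard error by about 3 to 21%, most plausibly 11 to 12%. Tanner stage should add to this, by an amount that the documents do not allow one to fix. Every growth input is assumed. The comparison is a safety analysis without multiplicity control (SAP 2.1), so no confirmatory claim depends on it. The case for acting is that the data are already collected and the change costs very little. The unstated reading count after Week 30 is a consistency gap and adds nothing to the main point.

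**What to change.** In SAP 4.6.4:

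- Add sex and baseline Tanner stage (grouped, for example 1–2, 3–4, 5), each with its interaction with visit, to the raw height and height-velocity models. A Week 30 ANCOVA with these terms is a simpler alternative.
- Add Tanner stage in the same way to the height SDS models.
- State which model height velocity uses.

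The cost is SAP wording and three model degrees of freedom per visit (one for sex, two for Tanner stage). SAP 4.1 would allow such an analysis later, but covariates fixed before unblinding are more credible than covariates chosen afterwards.

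Separately, state the number of height readings in the open-label schedule and in Appendix 11, to match the double-blind schedule. If triplicates are intended, this means two further readings at each of those visits. It does not affect the Week 30 comparison.

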4.6.5. Electrocardiograms

A listing of the abnormal selected ECG parameters will be produced in all mITT population. Descriptive statistics for the actual measurements and change from baseline, by treatment arm and scheduled visits will be performed for selected ECG parameters from baseline to follow-up using SS2.

QTcF will be used to correct the QT interval using the formulas below:

$$QTcF = QT/RR^{1/3}$$

The analysis of change from baseline in heart rate, PR interval, QRS interval, and QTcF will be conducted using an ANCOVA model with SS1 for double-blind period as specified in Section 4.1.5.4, without imputing any missing data.

Selected thresholds for QTc intervals are shown in Table GPGV.4.4 and will be used to summarize clinically relevant abnormal values for these variables from baseline to Week 30 and from baseline to safety follow-up.

Table GPGV.4.4. Thresholds for ECG Parameters of Interest

ECG Variable (unit)	Threshold
QTcF actual measurement (msec)	>460 (≤15 yrs), >450 (male, ≥16 yrs), >470
	(female, ≥16 yrs)
	>500
QTcF change from Baseline (msec)	>30, >60, >75
ECG heart rate (bpm)	Refer to pulse rate in Table GPGV.4.3.
PR Intervals (msec)	190 (10 to 12 yrs)
	210 (13 to 18 yrs)

Abbreviations: bpm = beats per minute; ECG = electrocardiogram; QTcF = Fridericia's corrected QT interval; yrs = years.

Note: PR intervals thresholds were provided by Lambrechts and Fourie (2000).

Threshold will be derived based on age at the time of assessment.

Arrhythmias and cardiac conduction disorders

PTs corresponding to these disorders are listed in the database in Appendix 1.

A summary of the incidence of arrhythmias and of cardiac conduction disorders will be provided with PT by treatment group from baseline to Week 30 using SS1 and from baseline to safety follow-up using SS2.

4.6.6. Special Safety Topics

AESI in this section may be known by alternative equivalent terms. A listing of search criteria for these AESI is provided in Appendix 1.

4.6.6.1. Hypoglycemic Events

Definitions and information on hypoglycemia are provided in Section 8.3.3.1 of Protocol GPGV.

Total hypoglycemia includes any event that meets criteria for documented symptomatic, severe, asymptomatic, or unspecified (that is, missing symptoms or signs, but with a blood glucose, BG, <70 or <54 mg/dL) whether daytime or nocturnal. Those categories that are defined by BG will be analyzed by the BG <70 and <54 mg/dL thresholds separately.

Total hypoglycemia category will have the following 2 subcategories:

- events with BG < 70 mg/dL included, and
- events with BG <54 mg/dL included.

To avoid duplicate reporting, all consecutive BG values <70 mg/dL (3.9 mmol/L) occurring within a 1-hour period may be considered as a single hypoglycemic event.

SS1 will be used for the primary analysis for hypoglycemia during Week 0 through Week 30, and SS2 for Week 0 through end of the treatment period (Week 52).

The incidence of hypoglycemic episodes will be summarized for each treatment group for 0 to 30 weeks, and 0 to the end of the treatment period. The summary includes the number of patients and percent of patients reporting hypoglycemic episodes. Fisher's exact test will be used for treatment comparison.

Counts of hypoglycemia or the rate of incidence of hypoglycemia episodes may be analyzed as described in Section 4.1.5.4 with a negative binomial regression model. The results will also be reported for the subset of participants who have baseline basal insulin use. All these analyses will be conducted excluding data after initiation of new antihyperglycemic therapy.

A listing of the individual hypoglycemic episodes will be presented from baseline to the end of the treatment period using SS2. Additional exploratory analyses may be performed if deemed necessary.

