ECG						X	X		Vital Signs must be taken before ECG, see Section 8.2.6
Review menstrual cycle history	X	X	X	X	X	X	X	X	All applicable female participants.
Participant Education			_						
Discussion of effective contraception	X	X	X	X	X	X	X		For males who have reached puberty and are sexually active, and for females of childbearing potential. For contraceptive guidance see Appendix 4, Section 10.4.
Review hypoglycemic events collected	X	X	X	X	X	X	X		Includes SMBG results, hypoglycemic events, date, and exact time of every study intervention injection.
Dispense BG meter/supplies as needed		X		X					Participant or parent or guardian will be trained as needed.
Lifestyle management instruction (ie, diet and exercise)		X		X		X			See Section 5.3.
Participant Diary (ele	ctronic)		•				•	•	
e-Diary return							X	X	
Laboratory Testing								•	
Hematology				X		X	X	X	See Appendix 2. Section 10.2
Clinical chemistry				X		X	X	X	See Appendix 2. Section 10.2
Lipid Panel				X		X	X	X	
Serum glucose				X		X	X	X	
HbA1c				X		X	X	X	
Pancreatic amylase				X		X	X	X	

FhStudy I8F-MC- GPGV			Open-	Label Per	iod			Follow-up Period	Notes
	Phone	Clinic	Phone	Clinic	Phone	Clinic	Clinic	Clinic	Type of visit.  Any phone visit may be converted to a clinic visit if deemed medically necessary by study personnel.
Visit	V14	V15	V16	V17	V18	V19	ET	V801	
Week	31	34	38	42	46	52		56	
Allowed Visit Intervals (D)	±3	±7	±7	±7	±7	±7		±7	
Fasting Visit						X	X		Participants should fast at least 8 hours without eating, drinking (except water), or performing any significant physical activity. The dose of insulin on a fasting visit may be adjusted upon clinical judgment of the investigator.
Lipase				X		X	X	X	
Thyroid-stimulating hormone (TSH)						X			
Thyroxine (T4, free)						X			
Calcitonin				X		X	X	X	
eGFR (CKD-EPI)				X		X	X	X	
Urinary albumin/creatinine ratio						X	X	X	
Serum pregnancy test				X			X		In females of childbearing potential only.
Urine pregnancy test	Xª	X	X*a	Х	Xª	X	X		If required per local regulations and/or institutional guidelines, pregnancy testing can also occur at other times during the study treatment period.  a If pregnancy is suspected, the participant should come to the clinic for this test. If a local urine pregnancy test is performed, collect serum pregnancy test at the same time and send to central laboratory.
Insulin						X	X		
Proinsulin, intact						X	X		
C-peptide						X	X		
Glucagon						X	X		
Adiponectin, total						X	X		

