# Tirzepatide

Tirzepatide is a dual GIP and GLP-1 receptor agonist that is currently being investigated for its potential use in the treatment of T2DM as a QW SC injection. Tirzepatide is a single molecule based on the GIP sequence and it includes a C20 fatty diacid moiety. It has a half-life of approximately 5 days enabling once weekly administration.

This study is designed to investigate the efficacy, safety, and PK/PD of tirzepatide (5 mg and 10 mg) in the pediatric and adolescent population aged 10 years to under 18 years with T2DM who have inadequate glycemic control, despite diet and exercise, with metformin or basal insulin, or both. The double-blind period of the clinical trial will last for 30 weeks and will test placebo against tirzepatide 5 and 10 mg SC injection QW. This will be followed by the 22-week open-label period of the clinical trial where all participants will receive either tirzepatide 5 mg/week or 10 mg/week, which will be followed by a 30-day safety follow-up period.

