## Visit 19 (end of open-label)

Upon completion of this visit, participants will stop taking tirzepatide and the participant's background diabetes medication should be adjusted.

Only metformin or insulin can be restarted or increased in dose as needed between Visit 19 and Visit 801.

A follow-up visual acuity check and dilated fundoscopic examination will be performed by an eye care professional (ophthalmologist or optometrist) within  $\pm$  21 days of this visit.

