# Early Termination and Safety Follow-up Visit

The participant will arrive at the clinic in a fasted state for Early Termination Visit. Safety Follow-up Visit is a non-fasted visit.

Participant and parent or legal guardian must return study equipment and devices (e-diary and glucometer) to the investigative site.

Participants discontinuing the study early should have the follow-up visit approximately 30 days after the early termination visit and should have a follow-up visual acuity check and dilated fundoscopic examination performed by an eye care professional (ophthalmologist or optometrist) within + 21 days of the early termination visit. If the early termination visit is scheduled within 6 months of the previous visual acuity check and dilated fundoscopic examination are not needed.

Participants who discontinue the study before randomization do not need to complete this visit.

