 To compare 5 mg, and 10 mg tirzepatide QW, analyzed as pooled and separate treatment arms, to placebo at 30 weeks, and To assess the effect of 5 mg and 10 mg tirzepatide QW, analyzed as pooled and separate treatment arms at 52 weeks 	 Incidence of new or worsening of dyslipidemia Incidence of new or worsening of hypertension Incidence of new or worsening of albuminuria Incidence of new or worsening of diabetic neuropathy Incidence of new or worsening of diabetic retinopathy or diabetic maculopathy in either eye 	
To assess safety of 5 and 10 mg tirzepatide QW, analyzed as pooled and separate treatment arms, at 30 weeks and through end of the safety follow-up period	 Treatment-emergent adverse events Discontinuation of study intervention due to AEs Adjudicated pancreatic AEs Serum calcitonin Incidence of allergic, hypersensitivity reactions, and injection site reactions Incidence of treatment-emergent anti-drug antibodies to tirzepatide Percentage change from baseline for serum lipid levels Change in systolic and diastolic blood pressure and heart rate from baseline Occurrence of hypoglycemic events Incidence of initiation of rescue therapy for severe-persistent hyperglycemia 	
 To compare 5 and 10 mg tirzepatide QW, analyzed as pooled and separate treatment arms, to placebo at 30 weeks, and To assess the effect of 5 and 10 mg tirzepatide QW, analyzed as pooled and separate treatment arms, at 52 weeks or end of the safety follow-up period 	 Change from baseline for physical and developmental measures height height SDS and weight SDS height velocity Tanner Staging 	
Characterize the pharmacokinetics and pharmacodynamic relationships of tirzepatide	Relationship between tirzepatide exposure and key safety and efficacy measures	
To assess the effect of 5 and 10 mg tirzepatide QW, analyzed as pooled and separate treatment arms, on patient-reported outcomes at 30 and 52 weeks	 Change from baseline for PedsQL Generic Core Scales PedsQL (3.2) Diabetic Module from baseline 	

Objectives	Endpoints
Tertiary/Exploratory	
 To compare 5 mg and 10 mg tirzepatide QW, analyzed as pooled and separate treatment arms, to placebo at 30 weeks, and To assess the effect of 5 mg and 10 mg tirzepatide QW, analyzed as pooled and separate treatment arms, at 52 weeks 	 Incidence of HbA1c ≤6.5% without clinically significant (blood glucose <54 mg/dL) or severe hypoglycemia Incidence of HbA1c <7.0% without clinically significant (blood glucose <54 mg/dL) or severe hypoglycemia

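### The safety objective for hypoglycemic events runs through safety follow-up, but the planned summary and listing stop at Week 52 and the schedule has no hypoglycemia review at Visit 801

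*SAP*

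**What the plan says.** SAP 1.1 lists "Occurrence of hypoglycemic events" under the objective to assess the safety of both doses, "analyzed as pooled and separate treatment arms, at 30 weeks and through end of the safety follow-up period". Protocol Section 3 pairs the same endpoint with the same two time points.

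SAP 4.6.6.1 then sets the hypoglycemia windows: SS1 from Week 0 to Week 30, and "SS2 for Week 0 through end of the treatment period (Week 52"). The incidence summary and the listing of individual episodes both end with the treatment period. The section also states: "All these analyses will be conducted excluding data after initiation of new antihyperglycemic therapy".

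In Protocol 1.3.2, the row "Review hypoglycemic events collected" is marked at Visits 14 to 19 and at early termination (ET). The Visit 801 cell is blank.

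Protocol 4.1.1 (Visit 19) stops tirzepatide, calls for background medication to be adjusted, and adds: "Only metformin or insulin can be restarted or increased in dose as needed between Visit 19 and Visit 801". Section 7.2 gives the same allowance between ET and Visit 801. The Introduction says of tirzepatide: "It has a half-life of approximately 5 days enabling once weekly administration".

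**The concern.** The objective names a period for which this endpoint has no dedicated analysis. The period is also one of changing risk: the study drug is washing out while background glucose-lowering treatment may be restarted or stepped up. The protocol itself treats basal insulin combined with study drug as a hypoglycemia risk (Sections 2.3.1 and 6.5.2).

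At stake is a descriptive safety statement in a pediatric trial. Level 1 and Level 2 episodes are defined by glucose value and recorded in the e-diary (Protocol 8.3.3.1). The analysis by the <70 and <54 mg/dL thresholds appears only in SAP 4.6.6.1. If that section stops at Week 52, families may keep recording episodes that no scheduled review or threshold-based table uses.

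**Working it through.** No sample size, power or error-rate figure bears on this point. The check sets the windows side by side, counts the schedule marks, and works out how much drug remains.

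**1. Windows**

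| Place | Content | Ends at |
|---|---|---|
| Protocol Section 3, SAP 1.1 | Objective containing hypoglycemic events | End of safety follow-up |
| SAP Table GPGV.3.1 | Data in SS2 | End of safety follow-up |
| SAP 4.6.6.1 | Incidence summary on SS2 | Week 52 |
| SAP 4.6.6.1 | Listing of episodes on SS2 | End of treatment period |
| SAP 4.6.2 | TEAE and SAE overview on SS2 | Safety follow-up |
| SAP 4.6.6.3, 4.6.6.6, 4.6.6.10, 4.6.6.12 | Pancreatitis, hypersensitivity, maximum severity of GI events, metabolic acidosis | Safety follow-up |

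The analysis set already holds the follow-up data; only the hypoglycemia section cuts them off. Between the protocol and the SAP, new or worsening hypertension, albuminuria and neuropathy were moved from the follow-up objective to a 52-week objective. Hypoglycemic events were left in the follow-up objective.

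**2. Schedule of Activities, Protocol 1.3.2** (eight columns: Visits 14 to 19, ET, Visit 801)

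- Hypoglycemia review: 7 of 8, with Visit 801 blank.
- Adverse events: 8 of 8.
- E-diary return: ET and Visit 801, so completers keep the diary until Visit 801.

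Protocol 4.1.1 asks for self-monitored glucose for the whole study, and Section 8.3.3.1 asks for each episode to be entered in the e-diary. For completers the data should therefore exist.

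**3. Length of the interval.** Week 52 to Week 56 is 4 of 56 weeks, or 4/56 = 7%, per completer.

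**4. Drug remaining.** Input: half-life of about 5 days (Protocol Introduction). Assumption: first-order decline from the last dose. Fraction left = 0.5^(t/5), with t in days.

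- t = 7: 0.5^1.4 = 37.9%
- t = 14: 0.5^2.8 = 14.4%
- t = 21: 0.5^4.2 = 5.4%
- t = 28: 0.5^5.6 = 2.1%

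The clock starts at the last dose, not at Visit 19. If that dose fell anywhere from 0 to 7 days before Visit 19 (assumption), 38% to 100% of it remains at Visit 19 and 0.6% to 1.6% remains 30 days later (t = 37 and t = 30). Residual exposure is material in the first two weeks and small by Visit 801.

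**5. The AE route.** Severe hypoglycemia must be reported as an SAE (Protocol 8.3.3.1), and AEs are collected until participation ends (Section 8.3.1). No passage requires each Level 1 or Level 2 episode to be reported as an AE, and SAP Appendix 1 has no hypoglycemia search. The AE tables therefore cannot stand in for the threshold-based summary.

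**The case against.** The strongest reply is that ending at Week 52 was deliberate. SAP 4.6.6.2 also stops rescue initiation, which sits under the same objective, at the end of treatment. SAP 4.6.6.1 leaves room for further exploratory analyses, and no primary or key secondary result is affected. This is a fair reading of intent, but it does not remove the contradiction. If Week 52 was intended, the objective is worded too widely.

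Three stronger readings are tempting, and the documents do not support them.

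- *Hypoglycemia after Week 52 goes unreported.* AEs are reviewed at Visit 801, severe events are SAEs, both enter SS2 summaries to follow-up, and completers still hold the e-diary. What is missing is the scheduled hypoglycemia review and the summary and listing by glucose threshold.
- *Early terminators have no means of recording because devices are handed in at ET.* Protocol 4.1.1 says families "must return study equipment and devices (e-diary and glucometer) to the investigative site", under a heading that covers both ET and the follow-up visit. The Schedule of Activities marks e-diary return at both and has no row for glucometer return. The timing is unclear rather than fixed at ET.
- *Anyone who restarts insulin drops out of the hypoglycemia analysis.* The exclusion concerns data after new antihyperglycemic therapy. The SAP does not say whether restarted or increased insulin counts as new, and SAP 4.1.8.1 lists insulin dose increases separately from initiation of new therapy. The exclusion sentence also precedes the listing sentence, so it may not govern the listing.

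Insulin changes in this interval are permitted as needed, so it cannot be assumed that insulin is raised in every participant.

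**Conclusion.** The mismatch is real and limited in scope. Followed as written, the plan leaves the follow-up part of a stated safety objective without its dedicated analysis for non-severe hypoglycemia. The gap is 4 of 56 weeks per completer and the roughly 4-week follow-up of participants who leave the study early.

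The contradiction itself rests on the text alone. Its clinical relevance rests on the documented half-life, the first-order assumption and the permission to restart or increase insulin or metformin. The drug-level figures describe exposure only; the documents give no event rate, so no count of missed episodes can be derived. The primary analysis, type I error control and sample size are untouched.

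**What to change.** 1. In SAP 4.6.6.1, run the descriptive SS2 hypoglycemia summary and the episode listing through the safety follow-up visit.
2. Show the post-treatment interval separately and without the new-antihyperglycemic-therapy exclusion. Extending the window alone might not recover these episodes, because the SAP leaves open whether restarted or increased insulin is new therapy. State which it is.
3. At the next protocol amendment, mark hypoglycemia review at Visit 801. Reconcile the Schedule of Activities with Protocol 4.1.1 on when early terminators return the e-diary and glucometer.
4. If the sponsor intends Week 52 as the cut-off, restrict the objective in Protocol Section 3 and SAP 1.1 to Week 52 for this endpoint instead.

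The cost is one extra descriptive table and a longer listing. The schedule change is small but is a protocol amendment requiring IRB/IEC approval (Protocol 10.1.1), so it is best bundled with the next one. The overall hypoglycemia count may rise slightly; a separate post-treatment display keeps that increase interpretable.
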